1.2 Schema

We will undertake a single arm feasibility study with n=20 patients with treatment naïve biopsy proven ILC who have either: a) clinical or imaging suspicion of metastatic disease; b) biopsy proven metastatic disease but in whom there is suspicion of an even greater tumor burden that could change therapy approach. All patients will be recruited from the Winship Glenn Family Breast Cancer Program at any Emory facility and they will have already undergone best standard of care conventional imaging (CT or MR and possibly bone scan depending on clinical presentation). **Standard of care conventional imaging typically does not include FDG PET, since FDG PET is not recommended for lobular cancer due to low sensitivity.** We will then complete both fluciclovine PET and Ga PSMA PET scans on the same patient on separate days separated by at least 10 half-lives to allow for radioactive decay. There is no need for randomization since each patient will undergo both imaging techniques, and the results will be interpreted blindly. Thus, radiopharmacy scheduling will dictate the order of the radiotracers to ensure the patient will undergo both imaging modalities in the shortest time frame. Sometimes this will mean PSMA is completed first, followed by fluciclovine, and other times the opposite. After interpretation of both studies, careful correlation to already obtained conventional imaging will then be done to determine if a previously unsuspected anatomic correlate can be identified which would impact therapy. One or two metastases (depending on scan findings) will then undergo biopsy in the safest manner possible as standard of care (if not already done) to determine the verified detection rate of metastatic disease. Uncommonly, definitive imaging such as MR for skeletal or liver lesions may be accepted in lieu of biopsy, if biopsy is not feasible. We will then compare verified detection rate of each PET study to conventional imaging and to each other. In addition, we will collect peripheral blood for ctDNA in all patients and determine if ctDNA correlates with presence or absence of metastases and tumor burden as identified by conventional imaging, fluciclovine and/or PSMA PET. Study Specific Experimental Procedures will only consist of both PET studies and ctDNA analysis. All other procedures will be conducted per standard of care. See Figure 1.

Figure 1: Trial Schema, Flow diagram

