2) MR: If a lesion is not deemed safe or possible to biopsy, MR may then be performed (e.g. for bone or liver). MR, even with the administration of Gadolinium is considered a safe and effective noninvasive imaging procedure. In addition to the small possible reactions to contrast material if used, claustrophobia while in the magnet is a potential risk, as well as reaction from metal within the body. Yet at Emory, special screening is performed before MR to determine if the patient has tattoos or any metal items in the body such as implants, pacemakers, clips or shrapnel, to make sure the MRI scan is done safely.

3. Objectives and Endpoints

3.1 Study Objectives:

Our major goal in this proposed investigation is to use advanced molecular imaging to better detect metastases in patients with invasive lobular cancer.

Specific Aim 1: Improve detection of metastasis with fluciclovine and Ga-PSMA PET versus best standard of care conventional imaging, as confirmed with histology. We will image 20 patients with ILC who have either: a) clinical or imaging suspicion of metastatic disease; or b) proven metastatic disease but in whom there is suspicion of an even greater tumor burden that could change therapy approach. Abnormal foci which correlate to anatomic lesions previously unsuspected on conventional imaging will undergo optional biopsy as clinically indicated in the safest manner possible (if not already done) to determine the verified detection rate of metastatic disease.

Specific Aim 2: Determine concordance and discordance of ILC detection with Ga-PSMA versus fluciclovine PET, as confirmed with histology. We will compare verified detection rates for metastasis between fluciclovine and PSMA PET modalities. This may necessitate a second biopsy of a distant lesion discordant between the 2 PET techniques. We will also analyze images for biodistribution in the primary lesion(s) for both radiotracers.

Exploratory Aim 3: Establish the role of molecular detection by ctDNA mutations including PIK3CA, ESR1, HER2, and AKT1 in characterizing the degree of tumor burden as identified by metabolic amino acid transport and/or tumor neovasculature receptor imaging [12]. We will collect peripheral blood for ctDNA in all patients and determine if ctDNA correlates with presence or absence of metastases and tumor burden as identified by fluciclovine (metabolic) and/or PSMA (angiogenesis) PET.

3.2 Study Endpoints:

Primary endpoint:

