4.1 Overall Design

We will undertake a study with 20 patients with treatment naïve biopsy proven ILC who have either: a) clinical or imaging suspicion of metastatic disease; b) biopsy proven metastatic disease but in whom there is suspicion of an even greater tumor burden that could change therapy approach. All patients will be recruited from the Winship Glenn Family Breast Cancer Program at any Emory facility. All patients will undergo Ga PSMA PET followed at minimum of 10 hours (to allow for radiotracer decay) by fluciclovine PET. (This may also happen in the opposite order, in which case 20 hours after fluciclovine will be needed to allow for decay.) There is no need for randomization since each patient will undergo both imaging techniques, and the results will be interpreted blindly. Thus, radiopharmacy scheduling will dictate the order of the radiotracers to ensure the patient will undergo both imaging modalities in the shortest time frame. Two nuclear medicine physician co-investigators, [name], will independently interpret the 20 cases, each reading half (the other reading the other half) of the fluciclovine and PSMA images (to avoid bias in always reading the same type of imaging). The readers will be blinded to all imaging including the other PET. All suspicious lesions with nonphysiologic activity above background for locoregional spread and distant disease will be identified and rated for suspicion of malignancy on a 6 point Likert scale (where 1 = definitely benign and 6 = definitely malignant). Both the primary lesion and all suspected metastases will be measured on an advanced workstation and metabolic uptake parameters (SUV, MTV, TLA) recorded. After both studies have been interpreted blindly, the third nuclear medicine physician co-investigator, [name], will blindly interpret **deidentified** PET studies on every patient (alternating for a total of 10 each fluciclovine and Ga-PSMA PET). Afterward, an unblinded reconciliation interpretation will take place with all 3 readers. To ensure balance, 10 of the studies will be reviewed for consensus first showing Ga-PSMA, then fluciclovine; 10 of the studies will be reviewed in the opposite manner. In this manner, a preliminary sense of kappa can be developed between the third and the other 2 readers, yet will guarantee the highest degree of patient care as there are currently no validated criteria for interpreting fluciclovine or PSMA PET for breast cancer. This approach will help us adapt existing prostate specific criteria to that of breast cancer. Concordant and discordant lesions between each PET study and conventional imaging will be reported and potential biopsy sites, if any, recommended. The most distant and accessible lesion may undergo biopsy in the safest manner possible (if not already done) as clinically indicated after discussion between the primary oncologist and patient.

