
Preference for biopsy will be given to discordant lesions. Uncommonly, in some lesions not deemed safe to biopsy, characteristic appearance on correlative imaging will be accepted as truth (e.g., MRI for certain skeletal or liver lesions). In select cases, a second biopsy of a discordant distant lesion may be required. For example, if there are 2 potentially impactful lesions which are fluciclovine positive/PSMA negative and fluciclovine negative/PSMA positive, respectively. Note that before biopsy is considered, careful scrutiny of the already obtained CT or MR will be undertaken to determine if an unsuspected anatomic correlate can be identified. This will then prompt a discussion between the patient and the referring clinician co-investigator on the benefits versus risks to definitively determine if a metastasis is present which could affect therapy. Biopsy may be undertaken in the least invasive manner as standard of care as clinically indicated, reimbursed by third party payers. Uptake parameters will be correlated with all proven primary, locoregional, and distant lesions. Verified detection rates for metastasis will be calculated for each modality.

In addition, we will collect 20 ml peripheral blood for ctDNA analysis in all patients at visit 1 (or possibly 2) to be initially processed and stored by [name] lab for off-site specialty analysis. Plasma levels of ctDNA will be measured using a targeted 28 gene panel to detect point mutations including mutations in PIK3CA, ESR1, HER2, and AKT1, genes associated with hormone therapy resistance and ILC [38, 39]. We will examine ctDNA results for association with presence or absence of locoregional metastasis on imaging as confirmed with histology, presence or absence of distant metastasis on imaging as confirmed with histology, correlation of presence or absence and absolute ctDNA with PET uptake.

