8.1 Schedule of Procedures

See above schedule of activities in Section 1.3 for **study specific experimental procedures**.

Standard of Care Procedures

1) Conventional imaging is broadly defined as mammography, ultrasound, bone scan, FDG PET, CT and/or MR: Any or all of these imaging studies may have been performed as standard of care at enrollment. These are not under control of study design. Conventional imaging and reports within 6 months of enrollment (ideally 2 months) will be reviewed to correlate to PET imaging. No additional interpretation will take place. Imaging reports for these studies will be utilized for comparative analysis.

2) Biopsy: After the PET studies, patients with abnormal findings on the PET scans will have the most distant and accessible lesion identified so that the patient may undergo biopsy in the safest manner possible (if not already done) as clinically indicated. Preference for biopsy will be given to discordant lesions. In some lesions not deemed safe to biopsy, characteristic appearance on correlative imaging will be accepted as truth (e.g., MRI for certain skeletal or liver lesions). In select cases, a second biopsy of a discordant distant lesion may be required. Note that before biopsy is considered, careful scrutiny of the already obtained CT or MR will be undertaken to determine if an unsuspected anatomic correlate can be identified. This will then prompt a discussion between the patient and the referring clinician co-investigator on the benefits versus risks to definitively determine if a metastasis is present which could affect therapy. Biopsy will be undertaken in the least invasive manner as standard of care, reimbursed by third party payers.

3) Therapy: All subsequent therapy for breast cancer will be standard of care and beyond the scope of this investigation.

9. Measurement of Effect

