Image Analysis: Two nuclear medicine physician co-investigators, [name], will independently interpret the 20 cases, each reading half (the other reading the other half) of the fluciclovine and PSMA images (to avoid bias in always reading the same type of imaging). The readers will be blinded to all imaging including the other PET. All suspicious lesions with nonphysiologic activity above background for locoregional spread and distant disease will be identified and rated for suspicion of malignancy on a 6 point Likert scale (where 1 = definitely benign and 6 = definitely malignant). Both the primary lesion and all suspected metastases will be measured on an advanced workstation and metabolic uptake parameters (SUV, MTV, TLA) recorded. After both studies have been interpreted blindly, the third nuclear medicine physician co-investigator, [name], will blindly interpret deidentified PET studies on every patient (alternating for a total of 10 each fluciclovine and PSMA PET). Afterward, an unblinded reconciliation interpretation will take place with all 3 readers. To ensure balance, 10 of the studies will be reviewed for consensus first showing Ga-PSMA, then fluciclovine; 10 of the studies will be reviewed in the opposite manner. In this manner, a preliminary sense of kappa can be developed between the third and the other 2 readers, yet will guarantee the highest degree of patient care as there are currently no validated criteria for interpreting fluciclovine or PSMA PET for breast cancer. This approach will help us adapt existing prostate specific criteria to that of breast cancer. Concordant and discordant lesions between each PET study and conventional imaging will be reported and potential biopsy sites, if any, recommended.

Correlation of histology with images: Uptake parameters as above will be correlated with all proven primary, locoregional, and distant lesions.

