ctDNA analysis: Plasma levels of ctDNA will be measured using targeted assays to detect point mutations including mutations in PIK3CA, ESR1, HER2, and AKT1, genes associated with hormone therapy resistance and ILC [12, 38, 39, 43]. Because ILC are predominantly hormone receptor positive, hormone resistance is particularly relevant because it predicts for higher rate of distant metastasis. [name], will provide expertise in ctDNA analyses. Deidentified specimens will be shipped to the Circulating Tumor Cell Center at Massachusetts General Hospital for fee for service ctDNA processing.

Correlation of ctDNA results with results of imaging: We will examine ctDNA results for association with presence or absence of locoregional metastasis on imaging as confirmed with histology, presence or absence of distant metastasis on imaging as confirmed with histology, correlation of presence or absence and absolute ctDNA with PET uptake as determined by the following indices: SUVmax, SUVmean, SUVpeak, Total Lesson Activity for the index primary, locoregional and distant metastatic lesion if any, and correlation to summed indices as a reflection of total metabolic tumor burden. ctDNA will also be correlated with CI.

10. Statistical considerations

Specific Aims 1 and 2

Analysis plan: The objectives of Aims 1 and 2 are to compare verified detection rates between fluciclovine and PSMA PET versus conventional imaging, as confirmed with histology (Aim 1), and determine concordance and discordance of ILC detection with PSMA versus fluciclovine PET, as confirmed with histology (Aim 2). Paired detection rates will be assessed using McNemar's test.

Detection rates will be reported for each method, and 95% confidence intervals will be estimated using the Clopper-Pearson approach. Rates of concordant/discordant observations will be reported. The Likert rating-scale data also allows for determination of sensitivity, specificity, PPV, NPV and Receiver Operating Characteristic (ROC) Area Under the Curve (AUC) values to compare.

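### Section 10 offers sensitivity, specificity, NPV and AUC from the Likert ratings, but ratings and verification are selective, so these values describe the rated and verified subset and not each PET's diagnostic accuracy

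*Combined protocol and SAP*

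**What the plan says.** Section 10 (Specific Aims 1 and 2, Analysis plan) gives McNemar's test and Clopper-Pearson intervals for detection rates, then adds: "The Likert rating-scale data also allows for determination of sensitivity, specificity, PPV, NPV and Receiver Operating Characteristic (ROC) Area Under the Curve (AUC) values", for comparison. It gives no unit of analysis for these measures, no Likert cut-off for a positive result, and no rule for unrated or unverified sites.

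The data come from the following provisions:

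- **Rating (sections 4.1 and 9).** "All suspicious lesions with nonphysiologic activity above background for locoregional spread and distant disease will be identified and rated for suspicion of malignancy" on a 6-point scale. No fixed list of regions is scored regardless of uptake.
- **Who is considered for biopsy (section 8.1).** "After the PET studies, patients with abnormal findings on the PET scans will have the most distant and accessible lesion identified".
- **Optional verification (section 3.1, Specific Aim 1).** "Abnormal foci which correlate to anatomic lesions previously unsuspected on conventional imaging will undergo optional biopsy as clinically indicated in the safest manner possible".
- **How many lesions (section 1.2).** "One or two metastases (depending on scan findings) will then undergo biopsy in the safest manner possible as standard of care". MR may uncommonly stand in for biopsy.
- **Which lesions (sections 4.1 and 8.1).** "Preference for biopsy will be given to discordant lesions". Discordance is used in two senses. One compares each PET with conventional imaging: "Concordant and discordant lesions between each PET study and conventional imaging will be reported and potential biopsy sites, if any, recommended". The other compares the two PETs, as in the second-biopsy example: "if there are 2 potentially impactful lesions which are fluciclovine positive/PSMA negative and fluciclovine negative/PSMA positive, respectively".
- **Follow-up.** Sections 1.3 (footnote e) and 4.4 provide medical-record follow-up, but do not name it as the truth standard for PET-negative sites. Aims 1 and 2 refer to confirmation by histology.

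**The concern.** Sensitivity needs the malignant sites that PET missed. Specificity and NPV need a fair sample of the sites that PET called negative. AUC needs a score on both diseased and non-diseased sites. Here both the score and, largely, the post-PET truth depend on the imaging result, which is partial verification. It also applies at patient level, because section 8.1 plans post-PET biopsy only for patients with abnormal PET findings.

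Reported as section 10 words it, these values would be read as each tracer's diagnostic accuracy. The pilot is meant to supply preliminary data for a definitive trial (sections 1.1 and 4.2), so unlabelled accuracy figures could be carried forward as though they were properties of the tests.

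**Working it through.** The plan gives no numerical value for sensitivity, specificity, NPV or AUC, so there is no figure to reproduce. Its McNemar sample sizes do not use these measures.

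**Which sites can have a score and a truth**

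| Site | Likert score on a given PET | Truth |
|---|---|---|
| Suspicious focus on that PET | Yes, possibly low | If biopsied, or MR accepted |
| Positive on the other PET only | None unless a low-suspicion focus was noted | If biopsied |
| Positive on conventional imaging, negative on both PETs | None unless noted | Earlier histology; possibly biopsy as a discordant lesion in a PET-abnormal patient |
| No uptake and no other finding | None | No rule; follow-up not named as reference standard |

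Some negatives therefore have a truth, but they are selected by other imaging or earlier clinical findings.

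**Illustration at site level. Every input is assumed; none comes from the documents.** Each PET and conventional imaging have sensitivity 0.6 and specificity 0.8, errors are independent, and half of candidate sites are malignant. True NPV = 0.8/(0.8 + 0.4) = 0.667; true PPV = 0.6/(0.6 + 0.2) = 0.75. The proportions below are within malignant or within benign sites; with equal prevalence they can be added directly for NPV and PPV.

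**Rule A: every lesion positive on either PET is verified.**
- Sensitivity = 0.6/(1 − 0.4²) = 0.6/0.84 = 0.714
- Specificity = (0.8 × 0.2)/(1 − 0.8²) = 0.16/0.36 = 0.444
- NPV = 0.16/(0.16 + 0.4 × 0.6) = 0.16/0.40 = 0.40
- With equal specificities, apparent specificity is Sp/(1 + Sp): true values of 0.7, 0.8 and 0.9 appear as 0.7/1.7 = 0.41, 0.8/1.8 = 0.44 and 0.9/1.9 = 0.47. Good and poor tests can hardly be told apart.

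**Rule B: low-suspicion foci are also rated and verified (80% of malignant, 40% of benign sites rated on each PET).**
- Sensitivity = 0.6/(1 − 0.2²) = 0.6/0.96 = 0.625
- Specificity = (0.64 − 0.20)/0.64 = 0.688
- NPV = 0.44/(0.44 + 0.36) = 0.55

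**Rule C: rule A, plus 25% of sites negative on both PETs.** This adds 0.25 × 0.16 = 0.04 of malignant and 0.25 × 0.64 = 0.16 of benign sites.
- Sensitivity = 0.6/(0.84 + 0.04) = 0.682
- Specificity = (0.16 + 0.16)/(0.36 + 0.16) = 0.615
- NPV = 0.32/(0.32 + 0.28) = 0.533

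**Rule D: only lesions discordant between one PET and conventional imaging are verified.**
- Sensitivity = 0.24/(0.24 + 0.24) = 0.50
- Specificity = 0.16/(0.16 + 0.16) = 0.50
- NPV = 0.16/(0.16 + 0.24) = 0.40

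**AUC.** In an equal-variance binormal model with the same inputs, d′ = 0.253 + 0.842 = 1.095 and the true AUC is Φ(1.095/√2) = 0.78. By simulation, rule A gives 0.66 among rated foci only and 0.64 with unrated sites scored lowest; rule B gives 0.69 and 0.70.

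**PPV.** It is 0.6/0.8 = 0.75 under rule A. If only half of the lesions positive on both PETs are verified, it is (0.18 + 0.24)/(0.18 + 0.24 + 0.02 + 0.16) = 0.42/0.60 = 0.70. It too is conditional on what is verified.

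| Verification rule | Sensitivity | Specificity | NPV |
|---|---|---|---|
| True (assumed) | 60% | 80% | 67% |
| A | 71% | 44% | 40% |
| B | 62.5% | 69% | 55% |
| C | 68% | 62% | 53% |
| D | 50% | 50% | 40% |

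**The case against.** The strongest reply is that the plan already speaks of verified detection rates and histological confirmation, that the wording in section 10 is permissive, that these measures are not listed endpoints, and that the study is small and exploratory. That stands as a limit on impact. It does not make the sentence correct, because nothing in it restricts these measures to verified lesions.

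A second reply is that PET-negative truth does exist. That also stands in part. Foci can be rated low, a lesion positive on one tracer can serve as a verified negative for the other, some lesions have earlier histology, and a lesion seen only on conventional imaging counts as discordant in one of the plan's two senses and may be preferred for biopsy in a PET-abnormal patient. A reader might infer that no PET-negative lesion will be verified, so that sensitivity is 100% and specificity 0% by construction; the documents do not support that. The negatives that are verified are still not a representative sample.

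A third reply is that follow-up of up to 5 years could supply truth. It could for some sites, but no passage makes it a reference standard, and the follow-up counted as sufficient in section 4.4 is undefined.

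Finally, the illustration is simpler than the plan. Rule A verifies every lesion positive on either PET, whereas section 1.2 foresees one or two biopsies; rule D treats a preference as a rule; and independent errors are assumed throughout. The figures show what selective verification can do and do not predict this trial's results.

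**Conclusion.** The concern holds for sensitivity, specificity, NPV and AUC: as planned, they describe the rated and verified subset and are not unbiased estimates of each PET's accuracy. On the assumed inputs, a true specificity of 80% appears as 44% to 69%, and a true sensitivity of 60% as 50% to 71%, depending on the verification rule.

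Two stronger readings should be resisted. A reader might infer that sensitivity is always overstated, or that the either-PET figures carry over when discordance means PET against conventional imaging. Neither follows. Rule D understates sensitivity. If the verified lesions are those positive on either PET and negative on conventional imaging (again 60%/80%), NPV is 0.128/(0.128 + 0.096) = 57% and PPV is 0.24/(0.24 + 0.16) = 60%, against 40% and 75% under rule A. A reader might also infer that the main results fail. The primary endpoint in section 3.2 is the verified detection rate, and neither it nor the future sample sizes in section 10 depend on this sentence.

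The change is worth making because it is cheap and alters what may be concluded, but its reach is limited to supplementary measures.

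**What to change.** Replace the sentence in section 10. Report verified detection rates, concordance and PPV, each labelled as conditional on verified lesions. Add one table of verified/total lesion counts by concordance pattern, for PET against PET and for each PET against conventional imaging.

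Do not present sensitivity, specificity, NPV or AUC as estimates of diagnostic accuracy. If they are shown, label them as descriptive of the verified subset, and state the Likert cut-off and how unrated sites were handled.

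The cost is some wording and one table. No extra readers, biopsies or patients are needed. The study gives up a claim to overall diagnostic accuracy, which its design does not support.
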